#### **4.7.3.3 Perfect-Use 7-Cycle Pregnancy Probabilities**

As a secondary evaluation of contraceptive efficacy, the 7-cycle cumulative pregnancy percentage of women in the EE population will be estimated by KM method. Each woman in the EE population is evaluated for efficacy for menstrual cycles when she has used the study product consistently and correctly as reflected in her diary recordings. Non-perfect-use and non-evaluable cycles will be removed from the analysis. The perfect-use analysis will use the same conventions and analysis rules mentioned for the typical-use analysis, except that non-perfect cycles with a pregnancy will not be included. Greenwood's method for calculating variance will be used to construct 95% confidence intervals.

#### **4.7.3.4 Pearl Rates from 7-Cycle Data**

The Pearl rate, also called the Pearl index ([Higgins 1985](#)), is defined as the number of pregnancies in 100 woman-years of method use.

Because this study will use natural women cycles and the days will vary from woman to woman, the primary method of analysis will be:

$$\frac{\text{Number of pregnancies} * 365.25 * 100}{\text{Total number of days exposed}}$$

For comparison, the Pearl rate will also be calculated using a 28-day cycle:

$$\frac{\text{Number of pregnancies} * 13 * 100}{\text{Total number of menstrual cycles}}$$

Both cycle-based and year based Pearl rates and their two-sided 95% CI will be presented, assuming a Poisson distribution. The Pearl rate will be done for the MITT and EE populations.

#### **4.7.3.5 Summary of Number of Diary Cycles and Cycles Excluded from EE Population**

The average number of diary cycles will be summarized for all MITT subjects through seven cycles. Diaries where backup contraception or EC were used will be excluded unless the subject became pregnant in that cycle. The number of cycles with incorrect use of study product which result in exclusion from the EE analysis will be calculated for each subject and summarized descriptively.

### **4.8 Safety Evaluation**

All safety analyses will be done for the Safety Population.

All laboratory data will be presented in the conventional United States (US) units.

Final evaluation is defined to be the last evaluation performed after the date of enrollment.

#### **4.8.1 Treatment Exposure**

Treatment exposure will be summarized for the Safety Population. Treatment exposure will be summarized by the number of times the treatments are used in acts of intercourse, the length of time over which the treatments are used, the number of times study product was used per cycle, and the number of cycles in the study. The number of times the treatments are used in acts of intercourse will be calculated as the sum of total number of intercourse acts where study product used as directed, total number of intercourse acts where study product not used as directed, and total number of intercourse acts with study product and other birth control. The length of time will be calculated as: last date study product was used – date of enrollment + 1. The number of cycles in the study will be the highest numbered cycle that started on or before the date of last study product use + 1 (the +1 is to account for cycle 0 (subjects are randomized mid cycle and that cycle is cycle 0)).

#### 4.8.2 Adverse Events

Incidence of adverse events will be summarized by SOC and PT. The number and percentage of subjects with each SOC and PT will be presented. Tables to summarize the incidence rates will be created for each of the following groups:

- Adverse events
- Serious adverse events
- Adverse events leading to premature discontinuation
- Adverse events by intensity
- Adverse events by relationship to study drug
- Adverse events by intensity and relationship to study drug (summary will present number of adverse events reported, not number of subjects)
- Adverse events presented in descending order of frequency by PT (no SOC shown)

If subject reports the same adverse event more than once, then that subject is only counted once for the summary of that adverse event, using the most severe intensity. The only exception to this will be for the summary by relationship to study drug. For that summary, if subject reports the same adverse event more than once, then that subject is only counted once for the summary of that adverse event, using the most severe relationship to study drug. The same principle will be applied at the body system level summary.

If intensity to study drug is reported as unknown, then the adverse event will be summarized as severe. If relationship to study drug is reported as unknown, then the adverse event will be summarized as certain/definite.

Adverse events that led to premature discontinuation from the study will be listed. Serious adverse events will also be listed. These listings will contain details about the adverse event such as intensity and relationship to study drug. Other supportive data, such as the subject's age, will be given.

A sensitivity analysis will also be performed for the Safety population to detect the differences between completers and non-completers with respect to adverse events.

All adverse events will be coded with MedDRA 21.0.

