An independent expert Pregnancy Review Committee will review all confirmed pregnancies. The Pregnancy Review Committee will determine if the pregnancy occurred on treatment (defined as date of conception between enrollment and <8 days after final study drug use) or not on treatment (defined as date of conception prior to enrollment or \geq 8 days following final study drug use), or whether there is insufficient information for adjudication. Subjects with an on-treatment pregnancy will discontinue drug but remain in the study for follow-up.

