- Review eDiary data report for completeness and accuracy, and assess the need for subject re-training in eDiary use
- Review study drug adherence data
- Review backup contraception use and sexual activity

- Collect unused study drug and unused applicators, and record study drug accountability information
- Re-supply study drug, as necessary
- Record concomitant medications (including any herbal or natural supplements)
- Record AEs
- Remind subjects of their right to use EC during the study
- Encourage subjects not to have intercourse, use the study drug, or place anything in the vagina within 24 hours of the next scheduled clinical site visit
- Visit 4 only: discuss post-study contraception with the subject to be started after completion of cycle 7 and before Visit 5/Exit Visit
- Schedule the next clinical site visit
- Confirm subject contact information

If the subject presents to an interim visit and is diagnosed with a UTI, symptomatic BV, trichomoniasis or symptomatic yeast vaginitis, she will be treated and allowed to continue in the study. All diagnosed or suspected conditions will be noted in the EDC system.

Based on gynecologic exam at each visit, investigators will note the presence or absence of vulvar, vaginal, or cervical findings (as defined in Section 5.4.3), including epithelial disruption, or areas of obvious erythema; these will be assessed as either not present, mild, moderate, or severe; the presence or absence of bleeding, petechiae, or sloughing will also be recorded on the gynecological exam eCRF. These findings will be reported as an AE if considered by the Investigator to be a clinically significant change from baseline, defined as an at least one level increase in severity of the finding from baseline.

If, during the eDiary review, the clinical site detects any pattern of incorrect or inconsistent drug usage, the subject will again be provided with proper usage instructions for the study drug. In addition, the eDiary data report will be reviewed to ensure that it does not contain reports of any signs or symptoms related to drug use. If a sign or symptom is reported in the subject eDiary that warrants follow-up, the subject may be contacted for further information as necessary and may be asked to return to the clinical site for evaluation and/or treatment.

At each interim visit, all subjects will be reminded to contact the clinical site as soon as possible if any of the following occur:

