5.4.2 Definitions

For the purposes of this study, an AE is any unfavorable and unintended sign (including abnormal laboratory finding), symptom, or disease temporally associated with the use of the study drug, whether or not it is considered related.

All AEs, including intercurrent illnesses, occurring during the study will be documented in the EDC system. Illnesses that existed before entry into the study will not be considered AEs unless they worsen during the treatment period. All AEs, regardless of the source of identification (e.g., physical examination, laboratory assessment, reported by subject), must be documented.

Pre-existing conditions will be recorded in the EDC system on the appropriate page (e.g., Medical History)

AE data should be collected from enrollment until Visit 5 (14-30 days after the seventh study cycle) or early termination from the study. Those events that occur between the Screening Visit and enrollment will be analyzed as medical history. A treatment-emergent AE (TEAE) will be defined as an AE that begins or that worsens in severity after at least one dose of study drug has been administered. All AEs considered at least possibly related to study drug will be followed until resolution or, for chronic conditions, until deemed stable.

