9.9.1 Incidence of Adverse Events

The number (percentage) of subjects with at least one AE will be presented in a frequency table by MedDRA system organ class and per MedDRA "preferred" term. A similar summary will be created for SAEs and AEs leading to discontinuation of study drug use. Summaries will also be presented by relationship to study drug and intensity of AE.

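### The adverse-event tables do not apply the protocol's own treatment-emergent definition and do not separate on-gel from off-gel time, and the final gynecological evaluation mixes the two

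*SAP*

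**What the plan says.** **Definition.** Protocol 5.4.2 states: "A treatment-emergent AE (TEAE) will be defined as an AE that begins or that worsens in severity after at least one dose" of study drug. It sets a start (first dose) and no end.

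**Collection.** The same section states: "AE data should be collected from enrollment until Visit 5 (14-30 days after the seventh study cycle) or early termination from the study".

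**Tabulation.** Protocol 9.9.1: "The number (percentage) of subjects with at least one AE will be presented in a frequency table". SAP 4.8.2: "Incidence of adverse events will be summarized by SOC and PT". SAP 4.8.2 then lists tables for all AEs, SAEs, AEs leading to discontinuation, AEs by intensity, by relationship, by both, and by frequency. None is restricted by time, and the term treatment-emergent does not occur in the SAP. The Safety Population (SAP 4.3) selects women with at least one application; it does not select events.

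**End of treatment.** Treatment ends after seven study cycles (footnote b to the schedule of assessments). At Visit 4, site staff "discuss post-study contraception with the subject to be started after completion of cycle 7 and before Visit 5/Exit Visit" (Protocol 5.1.3).

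**Pregnancy.** Protocol 4: "Subjects with an on-treatment pregnancy will discontinue drug but remain in the study for follow-up". The exit-visit timing under Figure 1 exempts women being followed for pregnancy. Pregnancy is not an AE; miscarriage and ectopic pregnancy count only if they meet an SAE criterion (Protocol 5.4.6 and 6.6).

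**Final evaluation.** SAP 4.8: "Final evaluation is defined to be the last evaluation performed after the date of enrollment". This row appears, with by-visit rows, in the gynecological examination tables (SAP 4.8.6).

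**The concern.** The gel is used on demand, so enrollment is not the start of exposure, and Visit 5 comes at least two weeks after treatment has ended. A table of all AEs from enrollment to Visit 5 therefore does not describe events under the gel. It also takes in events from time before any use, from time when another contraceptive may be in use, and from pregnancy after the gel was stopped. A reader cannot tell from the table which period an event belongs to.

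The final gynecological evaluation has a related problem. One row combines examinations made off gel with others made during use, and nothing in the label says so. In a single-arm study there is no comparator in which the same mixing would cancel, so the secondary safety objective depends on the tables saying which time they cover.

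**Working it through.** **1. The plan's own figures (Protocol 9.2, SAP 4.11.1).**
- Cycles: 1349 × (1 − 0.265) × 3.17 = 3,143.1. Plan: 3143.
- Completers: 1349 × 0.735 × (1 − 0.10 − 0.38) = 515.6. Plan: 515.

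Both reproduce. The first shows that the 3143 cycles described as evaluable for safety equal the efficacy-evaluable cycles of the 73.5% who qualify for the primary population. They are not a clean denominator for safety time, so the share is worked out per completer.

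**2. Post-gel share for one completer.** With cycle length L (21 to 35 days, the evaluable range) and gap g (14 to 30 days to Visit 5), the share of the time from the start of the first study cycle to Visit 5 is g / (7L + g).

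| L (days) | g = 14 | g = 30 |
|---|---|---|
| 21 | 14/161 = 8.7% | 30/177 = 16.9% |
| 28 | 14/210 = 6.7% | 30/226 = 13.3% |
| 35 | 14/259 = 5.4% | 30/275 = 10.9% |

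The range is about 5% to 17%. A woman whose study cycles are 1 to 7 also has up to 20 days of Cycle 0 after enrollment. Counting these moves the extremes to 14/279 = 5.0% and 30/197 = 15.2%. Last use may fall before the end of the seventh cycle, so the gap since last use can be longer than g.

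**3. All expected completers.** 515 × 14 = 7,210 and 515 × 30 = 15,450 woman-days, about 20 to 42 woman-years (÷ 365.25). Women who stop early and attend an exit visit 14 to 30 days after last use are not included.

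**4. Pregnancies implied by the planning rate.** Assume a constant hazard giving 16.5%, applied to 3143 cycles of 28 days (88,004 days). −ln(1 − 0.165) = 0.1803.
- 16.5% over seven cycles: 0.1803 / 7 × 3143 = 81.
- 16.5% over 183 days: 0.1803 / 183 × 88,004 = 87.

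Each of these women stops gel and stays in the study. The documents do not say how long AE collection lasts for her, so this time cannot be sized.

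**5. Before first use.** The documents give no time from enrollment to first application. This share cannot be sized either.

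**6. What the protocol's definition would change.** It has no end, so applying it removes only events before first use. Post-gel and in-pregnancy events remain treatment-emergent and can be told apart only by showing periods.

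**7. Final gynecological evaluation.** Examinations fall at Visit 3 (second study cycle), Visit 4 (fifth or sixth) and Visit 5. For a completer the last is Visit 5, off gel. For a woman without an exit examination it is Visit 3 or 4, normally during use. Both enter the same row.

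**The case against.** The case for leaving the plan alone is substantial.

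- **On-gel findings are shown elsewhere.** SAP 4.8.6 gives gynecological changes and graded findings at each visit. A worsening of one grade at any visit is to be reported as an AE (Protocol 5.1.3 and 5.4.3) and stays in the AE tables if it resolves. Genitourinary symptoms are recorded with each use and tabulated by time since application (SAP 4.8.3). A reader might infer that the final row hides local irritation; given these tables, the documents do not support that.
- **AEs are also tabulated by relationship.** A reader might infer that the tables attribute off-gel events to the gel. That goes too far: investigators record causality and other causes, and uncomplicated pregnancy loss is not an AE. Tabulating all AEs also tends to err against the product.
- **A share of time is not a share of events.** The tables report percentages of women, and nothing in the documents shows how far any percentage would move.
- **The plan has no on-treatment safety window to fall back on.** A reader might take last use plus 7 days as one. It is a rule for dating conception, and it starts at enrollment.
- **Vaginal pH does not belong in this point.** It is measured only in symptomatic women, and the Visit 5 procedure list omits it.

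All of this stands and lowers the weight of the point. It does not remove it. Relationship is a judgement, not a time, and an AE of unknown relationship is tabulated as certain/definite whenever it occurred. By-visit rows do not window the AE or SAE tables. The pre-treatment signs and symptoms table (SAP 4.5.6) leaves its period undefined and cannot cover time after gel. Collecting AEs after treatment is normal; the gap is that they are not separated.

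**Conclusion.** The point holds and is minor to moderate. The protocol defines treatment-emergent AEs and no planned table uses the definition. The main AE and SAE tables pool four kinds of time, and the final gynecological row mixes on-gel with off-gel examinations.

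The post-gel gap can be sized from the documents for completers: about 5% to 17% of the time from the first study cycle to Visit 5, or 7,210 to 15,450 woman-days if 515 women complete. This rests on cycles of 21 to 35 days and on Visit 5 falling within its 14 to 30 day window. The 81 to 87 pregnancies rest on the constant-hazard assumption and on efficacy-evaluable cycles, and indicate scale only. The time before first use and the time off gel in pregnancy remain unsized. No change in a specific AE percentage has been shown.

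CBC and chemistry are scheduled only at Screening and the exit visit, so completers' final values are off gel by design. They can be labelled, but an analysis window cannot change them.

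**What to change.** **SAP 4.8.2.** Base the main AE and SAE tables on the treatment-emergent definition in Protocol 5.4.2. Show AEs before first use, on gel, after last use, and in pregnancy in separate columns, so that no event is lost. State the cut-off that separates on-gel from post-use events before the data are analysed. Last use plus 7 days is one option; if chosen, say that it is borrowed from the conception rule and is not an existing safety window. Because gel continues until a pregnancy is confirmed, state which column takes an event between conception and last use.

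**SAP 4.8 and 4.8.6.** Report the last on-gel gynecological examination alongside the exit examination, and label Visit 5 as post-treatment there and in the laboratory tables.

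**Cost.** One derived period flag, a few extra columns, and probably a small shift in the headline AE percentage. No new data are needed: product use and AE dates are already collected, and SAP 4.10.1 already completes partial AE start dates by reference to the first dose.

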The Investigator will assess the causality/relationship between the study drug and the AE and record that assessment in the EDC system. The most likely cause of an AE (e.g., concomitant disease, concomitant medication, other) will be indicated in the EDC system with details of the concomitant disease or medication or other cause.

The causal relationship of the AE to study drug will be described per World Health Organization (WHO) Uppsala Monitoring Centre (UMC) causality categories¹⁵:

- Certain/Definite:
 - Event or laboratory test abnormality, with plausible time relationship to drug intake
 - Cannot be explained by disease or other drugs
 - Response to withdrawal plausible (pharmacologically, pathologically)
 - Event definitive pharmacologically or phenomenologically (i.e., an objective and specific medical disorder or a recognized pharmacological phenomenon)
 - Rechallenge satisfactory
- Probable/Likely:
 - Event or laboratory test abnormality, with plausible time relationship to drug intake
 - Unlikely to be attributed to disease or other drugs
 - Response to withdrawal clinically reasonable
 - Rechallenge not required
- Possible:
 - Event or laboratory test abnormality, with plausible time relationship to drug intake
 - Could also be explained by disease or other drugs
 - \circ $\,$ Information on drug withdrawal may be lacking or unclear $\,$
- Unlikely:
 - Event or laboratory test abnormality, with a time to drug intake that makes a relationship improbable (but not impossible)

- Disease or other drugs provide plausible explanations
- Not assessable:
 - Report suggesting an adverse reaction
 - Cannot be judged because information is insufficient or contradictory
 - Data cannot be supplemented or verified

Genitourinary Side Effects

Genitourinary (GU) side effects (including vaginal burning, vaginal itching, vaginal pain, and other unexpected vaginal symptoms) will be collected in the eDiary each time the study drug is used and will be recorded at AEs. Subjects will note the time of drug administration, time of sexual intercourse and if they had any side effect (including severity, duration, and resolution).

Unexpected vaginal bleeding or spotting will be recorded as AEs; however, expected menstrual-related bleeding and/or spotting will not.

Vulvar, Vaginal, or Cervical Side Effects

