6.4 Discontinuation of Subjects

A subject will be considered to have completed the study after she has completed seven on-study menstrual cycles (Section 3.3), the final visit has been performed, and the appropriate set of data has been collected and entered in the EDC system. A subject will be considered to have prematurely discontinued if she fails to remain in the study for seven on-study menstrual cycles and returns for Visit 5. Subjects who become pregnant while participating in the study are not considered to be discontinued unless they choose to no longer participate or are otherwise lost to follow up per Section 6.6. Subjects may withdraw from the study at any time without penalty and for any reason without prejudice to future medical care.

Subjects must be discontinued from the study for any of the following reasons:

- Withdrawal of consent
- Emergence of condition(s) such that, in the opinion of the Investigator, continuation in the study would negatively impact the health of the subject or would jeopardize the validity of the data collected (e.g., development of a condition that would have prevented her entry into the study according to the inclusion or exclusion criteria that could affect the study data)
- Any confirmed STI (other than HPV or trichomoniasis)

- Subject lost to follow-up
- If subject stops using study drug as her method of contraception
- Study terminated (Section 6.5)

Subjects may be discontinued prematurely from treatment for other reasons at the Investigator's discretion. Investigators considering subject discontinuation should contact the Sponsor/PAREXEL to discuss the specific case prior to withdrawal of the subject.

In all instances of premature discontinuation, the reason will be recorded in the EDC system. If withdrawal from the study is due to an AE, this information will also be recorded in the EDC system. In addition, all subjects who terminate early from the study will be asked to undergo the Treatment Exit Visit procedures (Section 5.1.4) regardless of the reason for discontinuation.

Every effort must be made to follow up with subjects who terminate with a study drug-related AE(s) to determine the outcome of the AE(s).

Subject Discontinuation Due to Non-Adherence

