#### 4.8.3 Genitourinary Side Effects

Genitourinary side effects will include vaginal discharge, vaginal burning, vaginal itching, vaginal pain, and other vaginal symptoms as reported by the subject in her eDiary. Partner side effects (burning, itching, pain, and other side effects) will also be captured in eDiary. Number and percentage of subjects with genitourinary side effects and partner side effects will be summarized in the following stratifications:

- By the time of symptom onset after product application
  - < 5 minutes
  - 5 – 30 minutes

- 31 - 60 minutes
- > 1 hour
- By the severity of the symptom
  - Mild
  - Moderate
  - Severe
- By duration of the symptom
  - < 5 minutes
  - 5 – 30 minutes
  - 31 – 60 minutes
  - > 1 hour

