##### 4.11.1 Determination of Sample Size

Simulation methods are used to evaluate the likelihood of various sample sizes providing enough information to test the primary hypothesis (one-sided Type 1 error of 0.025) and enough use cycles of Amphora gel to address other regulatory requirements. The six month (183 d) cumulative pregnancy percentage was estimated using Kaplan-Meier methods.

The sample size determination assumes the following:

- Study drug pregnancy percentage: 16.5%
- 26.5% of subjects fail to qualify for the primary efficacy analysis population
- Of the subjects that qualify for the primary efficacy analysis population, the average number of evaluable efficacy cycles per subject: 3.17
- Exponential hazard for:
  - Pregnancy rate first 6 months: 16.5%
  - Drop out month 1: 10%
  - Drop out months 2-6: 38%

With 1349 participants aged 18 through 35 years (inclusive), the study will have 90% power to ensure that the upper limit of the 95% CI of the cumulative seven-cycle pregnancy rate is less than or equal to 21%. The expected number of completers is 515 and the expected number of cycles evaluable for safety is at least 3143.

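### The planned completer versus non-completer AE comparison (SAP Table 14.3.1.8) makes no allowance for leavers' shorter time at risk, so it can hide a higher event rate in women who leave

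*SAP*

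**What the plan says.** SAP 4.8.2 plans a sensitivity analysis in the Safety Population "to detect the differences between completers and non-completers with respect to adverse events". The output is Table 14.3.1.8 in SAP 6.1. The sentence names no measure. The rule for AE tables in that section is "The number and percentage of subjects with each SOC and PT will be presented", and a woman with repeats of one event is handled as follows: "then that subject is only counted once for the summary of that adverse event, using the most severe intensity". SAP 4.2 makes number and percentage the default for discrete data. SAP 4.8.2 uses the term incidence rates, but neither document defines a person-time denominator or a time-to-event method for AEs.

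SAP 4.8.1 derives length of exposure (enrollment to last product use) but summarises it only for the Safety Population. It does not link it to AEs or split it by completion status. Protocol 5.4.2 collects AEs from enrollment to Visit 5 or early termination, so a woman who leaves early is observed for less time.

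The SAP does not define completer for this table. Three passages bear on it:
- Protocol 6.4 ties completion to seven on-study cycles, but adds "Subjects who become pregnant while participating in the study are not considered to be discontinued" (unless they stop participating or are lost).
- Protocol 9.8.3 counts a woman who conceives within seven cycles as a completer, for an efficacy sensitivity analysis.
- SAP 4.4.1 takes discontinuation status from the End of Study eCRF.

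**The concern.** The groups are formed by how long a woman stayed, and the measure rises with how long she was watched. The crude percentages will therefore differ even if the gel causes events at the same rate in both groups, and the difference will favour the leavers. The question behind the table is whether women who leave tolerate the product worse. A real excess in leavers is offset by their shorter observation, so the table could show no difference or a reversed one. Placement of pregnant women also matters, because they stop drug once pregnancy is confirmed (Protocol 6.6) and would add short exposure to whichever group receives them.

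**Working it through.** **The plan's own figures.** From SAP 4.11.1:
- 1349 × (1 − 0.265) = 991.5 women qualify for efficacy.
- 991.5 × (1 − 0.10 − 0.38) = 515.6, matching the stated 515 completers.
- 991.5 × 3.17 = 3143.1, matching the stated minimum of 3143 cycles. This is below 515 × 7 = 3605, so it cannot be used to derive leavers' exposure.

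**Leavers' time.** The inputs are 10% dropout in month 1 and "Drop out months 2-6: 38" per cent, each with an exponential hazard. Reading 38% as conditional on reaching month 2:
- Monthly hazards: −ln(0.90) = 0.105, then −ln(0.62)/5 = 0.096.
- Retained at month 6: 0.90 × 0.62 = 0.558, so 44% leave.
- Mean time on study up to month 6: 0.10/0.1054 + 0.90 × 0.38/0.0956 = 0.949 + 3.577 = 4.526 months.
- Mean leaver time: (4.526 − 6 × 0.558)/0.442 = 2.67 months.

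Reading 38% as a share of all women (48% leave) gives 2.69 months.

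**Completers' time (assumption).** Seven 28-day cycles: 196/30.44 = 6.44 months.

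**Ratio of time at risk.** 2.67/6.44 = 0.41. Adding an exit window of 14 to 30 days (0.46 to 0.99 months) to both groups gives 3.13/6.90 = 0.45 to 3.66/7.43 = 0.49.

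**Crude percentages at identical constant rates.** The monthly rate is −ln(1 − p)/6.44, where p is the completer percentage. The leaver percentage is the average of 1 − exp(−rate × t) over leaver times t. For p = 20% the rate is 0.0347. A check at the mean time gives 1 − exp(−0.0347 × 2.67) = 8.8%, and the full average is 8.7%. The window columns use 22 days, the midpoint of 14 to 30.

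| Completers | Leavers, no window | Ratio | Leavers, 22-day window | Ratio | Leavers with doubled rate (no window / window) |
|---|---|---|---|---|---|
| 10% | 4.2% | 2.4 | 4.8% | 2.1 | 8.2% / 9.4% |
| 20% | 8.7% | 2.3 | 9.9% | 2.0 | 16.3% / 18.6% |
| 40% | 18.3% | 2.2 | 20.9% | 1.9 | 32.0% / 36.5% |
| 60% | 29.5% | 2.0 | 33.6% | 1.8 | 47.5% / 53.9% |

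In every row a true doubling in leavers still looks lower than the completer figure. With no window, leavers would need 2.5 to 3.1 times the rate to look equal at completer percentages of 20-60%.

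**Events clustered early.** Let the month-1 hazard be k times the later hazard, the same in both groups. The later rate for p = 20% is 0.2231/(k + 5.44), with no window:
- k = 3: 20% against 10.9%, ratio 1.8.
- k = 10: 20% against 14.1%, ratio 1.4. Adding the 22-day window as well gives 15.6%, ratio 1.3.

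**Pregnant women counted as completers.** With a pregnancy hazard of −ln(0.835)/6 = 0.030 per month, the ratio of time at risk is 0.49-0.50. The crude ratio is 1.8-2.0 without the window and 1.6-1.8 with it.

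**Would one overall rate per woman-month cure it?** Only under a constant hazard, where the ratio is 1.00. With identical hazards in both groups, first events per woman-month show a spurious excess in leavers of about 1.27-fold at k = 3 and 1.65-fold at k = 10.

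**The case against.** Several stronger readings are tempting, and the documents do not support them.

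- A reader might infer that the percentage of women affected is the SAP's only AE measure. It is not: SAP 4.8.2 counts events in the table by intensity and relationship, and SAP 4.8.6 gives subjects and events for graded examination findings. Neither has a time denominator or is the completer table.
- A reader might infer that the SAP prescribes crude percentages for this comparison. That follows from the section's general rule and from SAP 4.2; the sentence itself is silent.
- A reader might infer that pregnant women fit neither group. Protocol 9.8.3 does class them as completers, though for an efficacy analysis, and the SAP does not carry this over.
- A reader might infer that the safety conclusion rests on this table. It does not: overall AEs (Table 14.3.1.1), AEs that led to discontinuation (Table 14.3.1.3 and Listing 14.3.2.2) and reasons for leaving (SAP 4.4.1) are reported independently.
- A reader might infer a firm twofold distortion. It is one scenario: early clustering, the exit window and placement of pregnant women all shrink it. Events that cause leaving push the other way, and that is the signal the crude comparison can cancel.
- A reader might extend the point to genitourinary symptoms, which "will be collected in the eDiary each time the study drug is used" but are reported in SAP 4.8.3 by women affected. That is a separate matter and not an error in this comparison.

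What stands is that none of these removes the difference in time at risk or changes its direction.

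**Conclusion.** The point holds as a weakness in a supportive table. If the section's general rule is applied, completers' crude percentage would be about 1.4 to 2.4 times leavers' at identical event rates, or about 1.3 if strong early clustering and the exit window are combined. A doubled rate in leavers could appear as 16-19% against 20%.

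The size rests on the planning dropout rates, 28-day cycles and, for the upper part of the range, a constant hazard. Those dropout rates are applied in the plan to women who qualify for efficacy. If the 26.5% who do not qualify are also early leavers in the Safety Population (assumed mean use 0.25 to 2.7 months), the ratio of time at risk would be about 0.26-0.45 and the distortion could be larger. The primary efficacy result is unaffected.

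**What to change.** In SAP 4.8.2 and Table 14.3.1.8:

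- Keep the crude percentage and show beside it each group's time at risk, from enrollment to the end of AE observation.
- Add AE incidence by study cycle: women with a first event in the cycle, divided by women under observation and still event-free at its start. Alternatively, give cumulative incidence censored at the end of AE observation. The second is cleaner for leavers, whose last cycle is usually incomplete.
- Do not rely on a single overall rate per woman-month, which misleads if events cluster early.
- State which group women with an on-treatment pregnancy belong to, reconciling Protocol 6.4, Protocol 9.8.3 and SAP 4.4.1, or show them as a third column.

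The cost is SAP wording, one derived variable and a few extra columns, with no new data. As a separate option, SAP 4.8.3 could add the percentage of gel applications followed by each symptom, with an interval that allows for repeated uses by the same woman.
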